6.4. Study population

Patients over 18 hospitalized in the ICU and presenting hypoxemia ($SpO_2/FiO_2 < 315$) and who have not been previously given chest physiotherapy on this ICU admission.

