7.4.5. LUS reporting to clinical physiotherapist and intensivist

The clinical physiotherapist and intensivist reviews the LUS report. Taking into account these LUS report, the clinical physiotherapist once again selects the chest physiotherapy treatment modalities indicated. The second chest physiotherapy treatment modalities will be recorded, with the reasons for a change of interventions (if indicated). The intensivist will again review any medical decisions that have been made. The new medical treatment for hypoxemia (or cause of hypoxemia) is recorded.

7.4.6. Second visit of the clinician physiotherapist: implementation of the chest physiotherapy treatment

After the review of the LUS report, the clinical physiotherapist may or may not decide to perform the chest physiotherapy treatment, to refer the patient to the intensivist, dependent upon his/her therapeutic strategy choice. The executed chest physiotherapy treatment provided will be recorded. The following data will be recorded:

- Current medical management:
 - o Oxygen therapy (and flow);
 - o Mechanical ventilation, NIV (PEEP, IPAP);
- Severity score: SOFA
- Vital signs: RR, HR, BP SpO₂, FiO₂ (true or estimated), body temperature, RASS, Glasgow coma score;
- Adverse effects during the chest physiotherapy treatment:
 - o Desaturation (< 4% of initial SpO₂);
 - o Decrease or increase of blood pressure (> 20% of initial SBP or DBP);
 - o Decrease or increase of heart rate (> 20% of initial heart rate);
 - o Endotracheal tube removal;
 - o Catheter or perfusion removal.

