7.4.8. Patient follow-up synthesis

	Pre-inclusion J 0	Inclusion J 0	First clinical physiotherapist visit J 0	LUS J 0	LUS results reading by the clinical physiotherapist and intensivist J 0	Second clinical physiotherapist visit J 0	End- research visit
Information consent	✓						
Demographic data		✓					
Reason for hospitalization, medical diagnosis if different		✓					
Medical management			✓			✓	
SAPSOFA , vital signs			✓			✓	
Medical diagnostic for respiratory condition		✓					
Medical treatment planned for respiratory condition		✓					
Clinical hypotheses of the clinical physiotherapist			✓		✓		
Choice of chest physiotherapy protocol			✓		✓		
LUS scan				✓			
LUS-scan report				✓	✓		
New choice of chest physiotherapy protocol						✓	
Adverse effect recording						✓	
New medical treatment planned for hypoxemia					✓		
ICU length of stay, duration of MV, vital status							✓

The data will then be entered in an e-CRF (Redcap.com) and analysed at the St. Joseph Hospital Network.

The statistical analysis will be conducted by the Clinical Research Centre (CRC) of the St. Joseph Hospital Network. An identifier will be attributed to each patient (initials of first name and family name – year of birth) and the data will be entered on an EXCEL file, which will be sent to the statistician in charge of the analysis at the St. Joseph Hospital Network.

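### The desaturation criterion in section 7.4.6 has an inequality that conflicts with its blood-pressure and heart-rate neighbours, and on either literal reading it leaves large falls unrecorded

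*Combined protocol and SAP*

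**What the plan says.** Section 7.4.6 of the combined protocol and SAP covers the second physiotherapist visit, when treatment is given. Under "Adverse effects during the chest physiotherapy treatment" it lists five items. Two are device removals with no numerical limit. The other three each name an event and then a percentage of the initial value:

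- "Desaturation (< 4% of initial" SpO₂)
- "Decrease or increase of blood pressure (> 20% of initial SBP or DBP")
- "Decrease or increase of heart rate (> 20% of initial heart rate")

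Desaturation is not defined anywhere else. The schedule in section 7.4.8 has a row "Adverse effect recording", ticked at the second visit, with no limit attached.

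**The concern.** Two of the three numerical items count changes larger than their limit; the desaturation item uses the opposite sign. If it is read as its neighbours are, it asks staff to record the smaller falls and pass over the larger ones.

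Desaturation is the only oxygenation item in the list, and every participant is hypoxemic at entry (section 5.1). The event is also one that occurs during treatment. Section 7.4.6 does not ask for the lowest SpO₂, so an event that is not flagged at the time may not be recoverable later. Section 10 mentions a follow-on randomised trial if the results are positive, and a usable adverse-effect record would help in planning it.

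**Working it through.** The 4% is a definition, not a derived figure, so there is no calculation in the plan to reproduce. The check is to apply the line literally and see which falls it catches.

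**Inputs.** The limit and its sign come from section 7.4.6. The initial SpO₂ values of 88%, 92% and 96% are assumptions, because the documents give no SpO₂ distribution, only the SpO₂/FiO₂ < 315 entry criterion.

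**Reading as a size of change.** Relative fall = (initial − current) / initial. From 92%:

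| Current SpO₂ | Fall (points) | Relative fall | Meets the line as written? | Would exceed 4% relative? |
|---|---|---|---|---|
| 91 | 1 | 1/92 = 1.1% | Yes | No |
| 89 | 3 | 3/92 = 3.3% | Yes | No |
| 88 | 4 | 4/92 = 4.3% | No | Yes |
| 84 | 8 | 8/92 = 8.7% | No | Yes |
| 80 | 12 | 12/92 = 13.0% | No | Yes |

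The last column keeps the sponsor's 4% and reverses only the sign, to show that the classification inverts. It is an illustration, not a proposed limit. The pattern is the same from 88% and 96%: tested falls of 1 to 3.5 points meet the line, and tested falls of 4 to 20 points do not. Reading the 4% as saturation points gives the same split in the as-written column.

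**Reading as a level.** SpO₂ would have to be below 4% of its initial value: 0.04 × 88 = 3.52%, 0.04 × 92 = 3.68%, 0.04 × 96 = 3.84%. None of the tested falls comes near this, so nothing would be recorded.

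**Reading as shorthand.** If the line stands for SpO₂ lower than its initial value by more than 4 points, tested falls of 5 points or more are flagged and smaller ones are not. This is the only reading tested that behaves as an adverse-effect criterion should, but it is not what is written.

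**Unit.** With the sign reversed, the relative and points readings part only narrowly. From 92%, a 4-point fall exceeds 4% in relative terms (4.3%) but does not exceed 4 points. From all three starting values, 4 points was the only tested fall on which they disagreed.

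**The case against.** The strongest reply is that the slip has little consequence. Adverse effects appear in no objective (section 3), no judgement criterion (section 4) and no planned analysis (section 8). Section 7.5 plans no monitoring, and section 7.6 ties stopping only to the exclusion criteria. The study has no comparator arm, so no safety contrast for ultrasound could be distorted. All of this stands, and it sets the size of the point.

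A second reply is that a critical care physiotherapist, seeing the word desaturation under an adverse-effects heading, will understand that a fall beyond 4% is meant. That is probably so, but a recording rule should not depend on the reader reversing its sign.

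Third, SpO₂ and FiO₂ are collected at both visits (sections 7.4.3 and 7.4.6), so some change can be derived whatever the flag says. This is partial cover, because the timing of the second reading relative to treatment is not stated. Fourth, the parallel wording of the other two items suggests that the 4% is relative, so the ambiguity of unit is minor. That is fair.

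A reader might go further and infer that the study's safety counts will in fact be wrong, that centres will diverge, or that the sponsor chose to record only small falls. The documents support none of these. They do not show how staff apply the line, the plan specifies no safety count as an output, the e-CRF is not among the documents, and nothing suggests that the sign was deliberate.

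**Conclusion.** The point holds as an internal inconsistency in a stated recording rule. The desaturation line conflicts with its two neighbours, nothing elsewhere corrects it, and on both literal readings (size of change and level) large falls during treatment go unrecorded. Which falls are recorded instead depends on the reading: small ones, or none. It would therefore go too far to state as fact that small falls will be recorded.

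The effect is limited to one item of the descriptive adverse-effect record. The NRI, kappa and the 150-patient target are unaffected. The numerical illustration rests on assumed starting saturations, but the direction of the result does not depend on them. A character error in the PDF text cannot be fully excluded, although the greater-than signs on the neighbouring lines came through.

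**What to change.** Reconcile the direction of the desaturation line in section 7.4.6 with the blood-pressure and heart-rate lines, so that all three count changes beyond the limit the sponsor has already stated. Say in the same line whether the 4% is relative to the initial SpO₂ or in saturation points. Check the e-CRF wording against the reconciled text and correct it only if it carries the same error. The limit itself is for the sponsor to set.

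The cost is one line of the protocol and a check of one e-CRF field, with no change to the sample size or the analysis. If patients have already been recorded under the present wording, note which reading the staff used before tabulating this item.

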7.4.7. End-research visit

When the patient is deceased or left the ICU, the following data will be recorded :

- ICU length of stay (day);
- Intubation (yes/no);
- Duration of mechanical ventilation (if adapted) (day);
- Number of extubation failure (if adapted) (yes/no);
- Vital status (alive/deceased);
- Duration of medical treatment present at the day of inclusion: antibiotics, hypnotics, opiates, steroids and anti-hypertensives (day).

7.4.8. Patient follow-up synthesis

	Pre-inclusion J 0	Inclusion J 0	First clinical physiotherapist visit J 0	LUS J 0	LUS results reading by the clinical physiotherapist and intensivist J 0	Second clinical physiotherapist visit J 0	End- research visit
Information consent	✓						
Demographic data		✓					
Reason for hospitalization, medical diagnosis if different		✓					
Medical management			✓			✓	
SAPSOFA , vital signs			✓			✓	
Medical diagnostic for respiratory condition		✓					
Medical treatment planned for respiratory condition		✓					
Clinical hypotheses of the clinical physiotherapist			✓		✓		
Choice of chest physiotherapy protocol			✓		✓		
LUS scan				✓			
LUS-scan report				✓	✓		
New choice of chest physiotherapy protocol						✓	
Adverse effect recording						✓	
New medical treatment planned for hypoxemia					✓		
ICU length of stay, duration of MV, vital status							✓

The data will then be entered in an e-CRF (Redcap.com) and analysed at the St. Joseph Hospital Network.

The statistical analysis will be conducted by the Clinical Research Centre (CRC) of the St. Joseph Hospital Network. An identifier will be attributed to each patient (initials of first name and family name – year of birth) and the data will be entered on an EXCEL file, which will be sent to the statistician in charge of the analysis at the St. Joseph Hospital Network.

7.5. Patient monitoring

None.

7.6. Research stopping rules

The definitive research stopping occurs when a patient meets the exclusion criteria. All of the study exit are defined and recorded in the CRF.

8. Statistical analysis

8.1. Calcul of number of subject

This is a pilot study and we don't have any information about the proportion of clinical decision modification in chest physiotherapy when the physiotherapist uses LUS information. The clinical experience of the investigators ([name] and [name]) allows to estimate an expected NRI of 30%. We want at least 50 events (clinical decision modification). So, we aim to include 150 patients in this study.

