8.2. Statistical method

8.2.1. Modification of the clinical decision chest physiotherapy

Calculation of the net reclassification index (NRI) (29):

$$\text{NRI (\%)} = (P_{\text{upevents}} - P_{\text{downevents}}) - (P_{\text{upnonevents}} - P_{\text{downnonevents}})$$

With:

Events: the results of the lung and diaphragm US are compatible with the clinical diagnosis for a clinical hypothesis.

Non Events: the results of the lung and diaphragm US are not compatible with the clinical diagnosis for a clinical hypothesis.

P_{upevents}: number of «events» when the LUS results modified the chest physiotherapy treatment modalities divided by the total number of «events».

P_{downevents}: number of «events» when the LUS results didn't modify the chest physiotherapy treatment modalities divided by the total number of «events».

P_{upnonevents}: number of «non-events» when the LUS results modified the chest physiotherapy treatment modalities divided by the total number of «non-events».

P_{downnonevents}: number of «non-events» when the LUS results didn't modify the chest physiotherapy treatment modalities divided by the total number of «non-events».

The significance test used will be the correlated proportions test (use of the properties of multinomial distribution). This is an asymptotic test for the hypothesis $NRI=0$.

$$z = \frac{\widehat{NRI}}{\sqrt{\frac{\hat{p}_{up,events} + \hat{p}_{down,events}}{\# \text{ events}} + \frac{\hat{p}_{up,nonevents} + \hat{p}_{down,nonevents}}{\# \text{ nonevents}}}}$$

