8.2.5. Modification of the intensivist clinical decision

Calculation of the net reclassification index (NRI):

$$\text{NRI (\%)} = (P_{\text{upevents-I}} - P_{\text{downevents-I}}) - (P_{\text{upnonevents-I}} - P_{\text{downnonevents-I}})$$

With:

Events: the results of the lung and diaphragm US are compatible with the medical diagnosis of intensivist for the patient respiratory condition for a clinical hypothesis.

Non Events: the results of the lung and diaphragm US are not compatible with the medical diagnosis of intensivist for the patient respiratory condition for a clinical hypothesis.

P_{upevents}: number of «events» when the LUS results modified the medical treatment for the patient respiratory condition divided by the total number of «events».

P_{downevents}: number of «events» when the LUS results didn't modify the medical treatment for the patient respiratory condition divided by the total number of «events».

P_{upnonevents}: number of «non-events» when the LUS results modified the medical treatment for the patient respiratory condition divided by the total number of «non-events».

P_{downnonevents}: number of «non-events» when the LUS results didn't modify the medical treatment for the patient respiratory condition divided by the total number of «non-events».

9. Justification for current care

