The expected benefit for patients is therefore that they will be given a chest physiotherapy protocol that is better suited to the type of respiratory dysfunction. This may include more optimal physiotherapy techniques for the patient, the decision not to intervene if physiotherapy is not indicated and more effective referral to the ICU physician in cases of doubt or suspicion of a condition that may warrant physician intervention.

If the results of this investigation are positive, we plan to conduct another randomised controlled trial, with patients allocated to chest physiotherapy guided by lung ultrasound or clinical examination alone, with the objective to evaluate the impact of the use of LUS on respiratory function, time on mechanical ventilation, mortality rates and hospital length of stay).

11. Risks for patients taking part in the study

No additional treatment or diagnostic studies are administered as part of this study. The lung and diaphragm US will be performed via the trans-thoracic approach. The examination is therefore non-invasive, completely painless and requires no exposure to radiation.

13. Funding

This study will be funded by the CHU de Dijon, the Forcilles' hospital and the Paris St Joseph Hospital Network for the French centre and by the University of Technology Sydney for the Australian centre. Funding will cover the time spent by the physiotherapist doing the LUS-scans, the time spent by the clinical research technician to collect the data, and by the CRA to monitor the study and take part in the statistical analysis.

14. Data recording in the Case Report Form

All of the data will be recorded in an e-CRF (<https://projectredcap.org>) and will be available for each investigator. All data will be anonymised.

15. Ethical and regulatory aspects

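### Under the 8.2.1 definitions, plan changes prompted by a contradicting scan make the primary NRI negative, which conflicts with the unsigned 30% expected in 8.1

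*Combined protocol and SAP*

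**What the plan says.** Section 4.1 makes the primary criterion a combination of two yes/no items, agreement of ultrasound with the clinical diagnosis and modification of the physiotherapy plan, summarised by the NRI.

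Section 8.2.1 defines an event as a case where "the results of the lung and diaphragm US are compatible with the clinical diagnosis for a clinical hypothesis", and a non-event as a case where they are not compatible. 'Up' means that treatment was modified after the scan and 'down' that it was not, each as a fraction of its own group. The index is (up − down) in events minus (up − down) in non-events, tested against zero with an asymptotic z statistic. Section 8.2.2 applies the same formula to subgroups. Section 8.2.5 applies it to the intensivist, with an event being a case where "the results of the lung and diaphragm US are compatible with the medical diagnosis of intensivist for the patient respiratory condition for a clinical hypothesis".

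Section 8.1 states that the investigators' experience "allows to estimate an expected NRI of 30"%, then "We want at least 50 events (clinical decision modification"), and concludes "So, we aim to include 150 patients in this study".

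Sections 6.5.1.4 and 6.5.1.5 with Annexe 2b have the physiotherapist choose treatment from the primary clinical hypothesis, and choose again after seeing the scan. Section 10 says "If the results of this investigation are positive, we plan to conduct another randomised controlled trial". No section says which sign of the NRI is favourable.

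**The concern.** An index of this kind is normally read with positive as good. Here, positive means that plans were changed more often when the scan confirmed the clinician than when it contradicted the clinician. Because treatment follows from the hypothesis, the opposite pattern is the one to expect from a useful scan, and that pattern yields a negative number. The planning value in 8.1 carries no minus sign.

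What is at stake is how the primary estimate is read. A clearly useful scan would produce an NRI opposite in sign to the figure used for planning, in a plan that does not say which direction counts as success. The subgroup indices in 8.2.2 inherit the same orientation.

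**Working it through.** **Inputs.** Formula, event, non-event, up and down: 8.2.1. Expected NRI 30%, 50 events and 150 patients: 8.1. The rates a and b below are illustrative assumptions, since the documents give none.

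**1. The plan's own figure.** Suppose the 30% is a modification proportion. Then 50 / 0.30 = 166.7, so 167 patients, and 150 × 0.30 = 45 modifications. The stated 150 corresponds to 50 / 150 = 33.3%. So 150 is not reproduced exactly, but it is close to what a modification proportion of about one third would give. No alpha or power is stated for the NRI test, so 150 cannot be derived from an NRI of 30% either.

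**2. The index in closed form.** Let a = proportion modified when ultrasound is compatible, and b = proportion modified when it is not. Down = 1 − up in each group, so

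NRI = [a − (1 − a)] − [b − (1 − b)] = (2a − 1) − (2b − 1) = 2(a − b).

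The range is −200% to +200%, and the sign depends only on whether a exceeds b.

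**3. Values.**

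| a (compatible) | b (not compatible) | NRI |
|---|---|---|
| 0% | 100% | −200% |
| 15% | 60% | −90% |
| 20% | 35% | −30% |
| 30% | 30% | 0% |
| 35% | 20% | +30% |
| 100% | 0% | +200% |

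The first row is perfect use of the scan: every contradicted plan changed, every confirmed plan kept.

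**4. What an NRI of 30% requires.** 2(a − b) = 0.30 gives a − b = 0.15: modification 15 percentage points more frequent after agreement than after disagreement.

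**5. What a 30% proportion modified would imply for the sign.** Nothing. With 75 compatible and 75 non-compatible cases, a = 22.5% and b = 37.5% average to 30% and give NRI = 2(0.225 − 0.375) = −30%. Exchanging the two rates also averages to 30% and gives +30%.

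**6. Effect on the test.** Up + down = 1 in each group, so the denominator in 8.2.1 is √(1/events + 1/non-events). Exchanging the two definitions leaves it unchanged and reverses the numerator. For a = 15%, b = 60% at 75/75, z = −0.90 / √(1/75 + 1/75) = −5.5 as written and +5.5 after the exchange. For an index of 30% in size, |z| is 0.30 / √(2/75) = 1.84 at 75/75 and 0.30 / √(1/50 + 1/100) = 1.73 at 50/100 or 100/50, whichever the sign. A two-sided p-value does not change.

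**The case against.** A reader might infer that 8.1 plans for the opposite of the study's hypothesis and that a favourable result would be declared unfavourable. The documents do not support that.

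- **The hypothesis has no direction.** Section 2 says only that ultrasound findings will change treatment decisions. That b exceeds a is an inference from 6.5.1.4, 6.5.1.5 and Annexe 2b.
- **The inference is not watertight.** In Annexe 2b some hypotheses share treatments: the unilateral, non-intubated entries for pneumonia and for pleural effusion list the same measures, and several rows lead to medical referral. A contradicted hypothesis can therefore leave the plan unchanged. Treatment also varies with side and extent, so a compatible scan can change it. This narrows the gap between b and a but gives no reason to expect a to exceed b.
- **The 30% may not be a signed expectation.** Section 8.1 speaks of the proportion of decisions modified just before it and counts modifications as events just after it, and 50/150 is 33%. A mislabelled proportion is a credible reading. It still needs correcting: the figure is called an NRI, 8.2.1 is the NRI's only definition, and 'events' means modifications in one section and compatible scans in the other.
- **No decision rule goes wrong.** The plan specifies no one-sided test and no comparison with +30%, and section 10 does not tie a positive study to the sign of the NRI. The component rates are defined, so the direction could be recovered, although 8.2.4 only adds them together.
- **Section 8.2.5 is a weaker case.** Its formula and event definition have the same form, but nothing maps the intensivist's diagnosis to medical treatment.

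It is also true that reversing the sign does not make the index measure how often decisions change: it is 0 whenever a = b, whether every plan changes or none does.

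**Conclusion.** The point holds as a conflict between the primary formula and its planning value. That NRI = 2(a − b) is exact and rests on no assumed rate. That the expected sign is negative rests on the protocol's link from hypothesis to treatment, which makes b > a likely but not certain. An NRI of 30% as defined requires a to exceed b by 15 points, which runs against that link. If the 30% is really a proportion modified, the fault is a mislabelled quantity and a word used in two senses. Either way 8.1 and 8.2.1 cannot both stand as written.

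The consequence is one of interpretation: a primary estimate likely to carry the opposite sign to its planning value, with no statement of which sign is good. The size of the estimate, |z| and a two-sided p-value are unaffected. The documents do not show that a useful scan would be declared a failure.

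**What to change.** - In 8.2.1 and 8.2.2, and in 8.2.5 for consistency, define events as ultrasound not compatible and non-events as ultrasound compatible, or keep the definitions and reverse the subtraction. Perfect use then scores +200%.
- State that a positive value is the favourable direction, and say in section 10 what a positive result means.
- Report a and b alongside every index, so that direction and overall frequency of change are both visible.
- In 8.1, replace the 30% with the expected a and b or, if that was the intention, with the expected proportion of decisions modified under that name. Use 'events' in one sense throughout.
- Do not simply rewrite the figure as −30%. Nothing in the documents supports that value, and it would turn a possible proportion into a signed index.

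The cost is wording in the statistical sections and section 10. Data collection and the size of the test statistic do not change, and the re-orientation itself does not alter the 150 patients. The change should be made before the primary analysis is run.

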 - When the findings from a chest CT-scan less than 12hours old are available;
 - For each clinical hypotheses;
 - For each level of certainty of clinical hypothesis;
 - For type of patients (reasons for admission the most represented);
 - For each research center.
2. Determine the level of agreement between the physiotherapist's diagnosis comparing the clinical vs LUS findings, overall, for the level of certainty of clinical diagnosis and for the population where a CT-scan is available;
3. Determine the frequency of changes in the chest physiotherapy following the assessment of the LUS results, overall and for each type of clinical hypothesis;
4. Determine the frequency of changes in the medical treatment (determined by intensivist) following the assessment of the LUS results performed by the physiotherapist, overall and for each type of clinical hypothesis.

4. Judgement criteria

4.1.Principal judgement criterion

Modification of the clinical decision: agreement (yes/no) between the lung and diaphragm US diagnosis and the clinical diagnosis and modification (yes/no) of the chest physiotherapy protocol, expressed using the Net Reclassification Index (NRI).

4.2.Secondary clinical decision-makingjudgementcriteria

1. Modification of the clinical decision:
 - When a chest CT-scan < 12h is available;
 - For each clinical hypotheses;
 - For the level of certainty of clinical hypotheses (Likert scale: strongly certain, certain, neither certain nor uncertain, uncertain, strongly uncertain);

- For type of patients (reasons for admission the most represented);
 - For each research center.
2. Proportion of agreement between clinical and LUS diagnosis:
- Overall;
 - For the level of certainty of clinical hypotheses (Likert scale: strongly certain, certain, neither certain nor uncertain, uncertain, strongly uncertain);
 - When chest CT-scan < 12h is available.
3. Proportion of cases when the chest physiotherapy protocol is modified following the results of the LUS:
- Overall;
 - For each type of clinical hypothesis;
 - When a chest CT-scan < 12h is available;
4. Modification of the clinical decision of intensivist:
- Overall;
 - For each type of clinical hypothesis;
 - When a chest CT-scan < 12h is available.

5. Inclusion/exclusion criteria:

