6.5.2.4. Lung and diaphragm ultrasound report

The physiotherapist/operator will write a detailed LUS-scan report, which will be given to the clinical physiotherapist. When LUS is performed by a french physiotherapist, the LUS report will be checked and validated by the referent intensiviste.-The LUS-scan report# will include the LUS and Diaphragm diagnosis and describe the signs observed in the different regions of the chest (*cf. annexe4*). The clinical physiotherapist is trained to interpret LUS reports. The clinical physiotherapist then determines the options or changes to treatment based on the US findings.

7. Studyprogress

7.1.Study planning

- Ethic comittee submission: December 2016;
- Study comencement: January 2016;
- Inclusion duration : 12 months;
- Length of patient participation: one day;
- End of inclusion: January 2017;
- Total duration of the study: 18 months;
- Congress communications: French Intensive Care Society Congress, ESICM, ERS, ATS, from April 2018;
- Publication: September 2018;
- Target journal: Physical therapy, Intensive Care Medicine or Critical Care Medicine.

7.2.Recruitment method

Patients will be recruited in the Surgical ICU of the CHU de Dijon, Medical-Surgical ICU of Paris St. Joseph's Hospital, Respiratory ICU and Post-ICU Rehabilitation Unit of Forcilles' Hopital and the ICU of St Vincent's Hospital.

Patients admitted to the ICU and who meet the inclusion criteria will be invited to take part in the study. Patients with hypoxemia will be identified by the duty physician at the time of

transfer to the unit or by the principal investigator and the coordinating investigator during the day. Written informed consent will be collected (*cf. annexes 5a and 5b*).

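### The sample size of 150 does not follow from the expected NRI of 30% and the target of at least 50 modifications, because an NRI fixes no number of modifications

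*Combined protocol and SAP*

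**What the plan says.** Section 8.1 is the only justification of the sample size. It calls the study a pilot and says that "we don't have any information about the proportion of clinical decision modification in chest physiotherapy" is available. It reports that the investigators' experience "allows to estimate an expected NRI of 30" percent. It then states the target and the conclusion: "We want at least 50 events (clinical decision modification). So, we aim to include 150 patients in this study".

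Section 4.1 makes the principal criterion agreement and modification "of the chest physiotherapy protocol, expressed using the Net Reclassification Index (NRI"). Section 8.2.1 defines the terms:

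- "Events: the results of the lung and diaphragm US are compatible with the clinical diagnosis for a clinical hypothesis". Non-events are the cases where they are not compatible.
- In each group, the up proportion counts cases whose treatment was modified. The down proportion counts cases where the "LUS results didn't modify the chest physiotherapy treatment modalities divided by the total number of" that group.
- A z statistic is given, with the comment "This is an asymptotic test for the hypothesis" that the NRI is zero.

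Section 8.2.4 reports the proportion modified, written as the sum of the two up proportions, with a confidence interval at alpha 0.05.

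**The concern.** Turning a wanted number of modifications into a number of patients takes a modification rate. Section 8.1 says that this rate is unknown, and no other section supplies one. The 30% it does give is an NRI, which is a different quantity. A reader therefore cannot tell what rate lies behind 150, how likely the study is to reach its own target, or how precisely the modification proportion will be estimated.

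The wording adds to the problem. In section 8.1 an event is a modified decision. In section 8.2.1 it is an ultrasound result compatible with the clinical diagnosis. The target of 50 could be mistaken for the number of events in the NRI denominator.

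**Working it through.** **Inputs.** From section 8.1: N = 150, expected NRI = 0.30, target of at least 50 modifications. From section 8.2.1: the NRI formula, the definitions of up and down, and the z statistic. From section 6.5.1.5: treatment is chosen for the primary hypothesis, so I count one decision per patient. The documents give no modification rate, no split between compatible and non-compatible cases, and no alpha or sidedness for the NRI test. Values for these are assumptions.

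**1. Trying to reproduce 150.** The only direct route is target divided by rate.
- 50 / 0.30 = 166.7, so 167 patients, not 150.
- 150 × 0.30 = 45, not 50.
- 50 / 150 = 0.333. Only a rate of one third gives 150, and it is not stated.
- An allowance for losses moves N further away: 167 / 0.90 = 185.6, so 186 at 10%.

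**2. What an NRI of 30% fixes.** Let u1 and u0 be the modification rates among events and non-events. Every case is either modified or not, so down = 1 − up in each group, and

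NRI = [u1 − (1 − u1)] − [u0 − (1 − u0)] = 2(u1 − u0).

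Setting this to 0.30 gives u1 − u0 = 0.15.

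**3. Modification counts compatible with it.** The expected count is n1·u1 + n0·u0, with u1 = u0 + 0.15 and u0 anywhere from 0 to 0.85.

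| Assumed split (events/non-events) | Lowest | Highest |
|---|---|---|
| 75/75 | 75 × 0.15 = 11.25 | 75 × 1 + 75 × 0.85 = 138.75 |
| 50/100 | 7.5 | 135 |
| 100/50 | 15 | 142.5 |

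At 75/75, rates of 20% and 5% give 18.75 modifications, 40% and 25% give 48.75, and 95% and 80% give 131.25. All three pairs have an NRI of 30%. A negative NRI of the same size leaves the 75/75 range unchanged and exchanges the other two.

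**4. If 30% was meant as a rate.** With independent patients the count is binomial.
- N = 150, rate 0.30: expected 45, P(at least 50) = 0.210.
- N = 150, rate 1/3: expected 50, P(at least 50) = 0.531.
- N = 167, rate 0.30: expected 50.1, P(at least 50) = 0.536.
- For an 80% chance of at least 50: N = 183 at 0.30 (0.807), or N = 164 at one third (0.803).

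**5. Precision at 150.** For total modifications divided by 150, the 95% half-width is 1.96·√[r(1 − r)/150]: 7.3 points at r = 0.30 and 7.5 points at one third. The sum written in section 8.2.4 is a different quantity. At 75/75 with 30% in each group its half-width is 1.96·√(2 × 0.30 × 0.70/75) = 14.7 points.

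**6. Power of the NRI test at 150, if the 30% is a true NRI.** Because up + down = 1, the plan's statistic reduces to z = 2(û1 − û0)/√(1/n1 + 1/n0). At 75/75 the denominator is √(2/75) = 0.163, so the expected z is 0.30/0.163 = 1.84. Against a cut-off of 1.96 (two-sided alpha 0.05 assumed) the normal approximation gives about 45% power.

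Exact enumeration of two independent binomials, over the same range of u0, gives:
- 75/75: 33% to 42%.
- 74/76: 35% to 47%.
- 50/100: 33% to 43%.
- 30/120: 5% to 30%.

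The jump between 75/75 and 74/76 comes from discreteness. At 75/75 a difference of 12 patients gives z = 1.9596, just short of the cut-off. Repeating the enumeration at every whole-number split from 50/100 to 75/75 never exceeds 47%. A few splits fall below 33%, the lowest being 27% at 54/96, and only when one group's rate is at or near 0% or 100%.

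**The case against.** The best defence is that this is a declared pilot that openly admits having no prior information. A sample size based on experience is ordinary in that setting, and the absence of a power calculation is not in itself an error. This stands. But section 8.1 does more than state a round number. It presents 150 as the consequence of two inputs that do not yield it.

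A second defence is that 30% is one third, loosely rounded. The gap between 150 and 167 is then small. The text, however, calls the figure an NRI and states no rate of one third. Even at that rate, at least 50 is little better than an even chance.

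Third, the numerical results rest on assumptions. The binomial and precision figures assume independent patients, whereas section 7.2 lists units in several hospitals and individual physiotherapists choose the treatment. Clustering would change these figures. The power figures depend on the split, and narrow ranges tied to one exact split should not be quoted as firm. One-sided figures are left out because they depend on a direction that the plan does not state. None of this touches steps 1 and 2.

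Three stronger readings are tempting.
- *The plan gives no alpha at all.* It does: section 8.2.4 gives 0.05, for a confidence interval. The accurate statement is that no alpha or power is tied to the NRI test or to N.
- *The later randomised trial hangs on a significant NRI.* Section 10 makes that trial conditional on positive results but does not define positive.
- *The sample size must be raised.* The plan gives no reason why 50 modifications are needed, so nothing in it shows that 150 is too few for a pilot.

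**Conclusion.** The concern holds. The stated inputs do not produce 150, and the stated target is not what 150 patients can be expected to deliver at any rate that the plan gives. Read as defined, an NRI of 30% leaves the expected number of modifications anywhere from about 11 to 139 (75/75 split assumed). Read as a rate, it gives 45 expected modifications and a 21% chance of at least 50 (independent patients assumed).

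A reader might infer that the authors simply mislabelled a modification rate as an NRI. The text does not say so, and it states that the rate is unknown, so that reading can only be offered conditionally.

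The failure of the derivation is algebra and arithmetic and needs no assumption about split, alpha or clustering. The statement that the NRI test has under 50% power applies only if the 30% is kept as an NRI, and it rests on a two-sided alpha of 0.05.

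**What to change.** In section 8.1:

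1. Stop deriving the number of modifications from the NRI. State the modification rate used and label it an assumption.
2. Keep N = 150 and replace the minimum of 50 with the expected number at that rate: 45 at 30%, 50 at one third.
3. Give the 95% half-width for total modifications divided by 150 (7.3 points at 30%, 7.5 at one third, independent patients assumed). Say that this is the overall proportion and not the sum of the two up proportions in section 8.2.4.
4. Write modifications in section 8.1 and keep events for the meaning in section 8.2.1.
5. If the NRI of 30% is kept, state that N was not sized for the NRI test and that its power at an assumed two-sided alpha of 0.05 is below 50%. It is roughly 33% to 47% for most splits between 50/100 and 75/75, and lower for more uneven splits or for rates near 0% or 100%.

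The change is to wording only and needs no extra patients. Its cost is a slightly less favourable stated target and, if item 5 applies, open disclosure of low power for the test of the principal criterion.
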